6.3.2 Paraffin block/slide collection and processing for histopathology review

Consistent and accurate assessment of AR status is important for study eligibility. Submission of paraffin blocks or slides from a diagnostic tumor biopsy or surgery is required for all patients enrolled to this study. All tissue will be sent to Memorial Sloan Kettering. All samples should be labeled with institutional surgical pathology number (tumor samples), study number, patient ID number patient initials, sample collection date and time per section 6.2.1.

Blocks which contain minimal amounts of tissue specimen or that are very thin should not be submitted unless the block is the only representative tissue for the case. A de-identified surgical pathology report should be sent with all specimens. Usually, this is generated by obscuring all PHI (names and dates) with white-out or a black magic marker, labeling each page of the report with the Alliance patient ID, and photocopying the report. In addition to the pathology report, the institution must complete and submit the "Central Pathology Review Form and AR Testing Form" with the tumor block or slides to Memorial Sloan Kettering Cancer Center. Failure to submit this form with the specimens will delay turnaround time for central pathology review. The top portion of the form must be completed by typing and cannot be handwritten. For Alliance members, the form may be found on the A091404 study page on the Alliance website under the "Supplemental Materials" tab. For non-Alliance institutions, the form can be found under "Miscellaneous" documents section of the CTSU A091404 study page (www.ctsu.org). When shipping blocks and /or FFPE slides, it is important to avoid extreme heat. If environmental conditions indicate, specimens may be shipped in containers containing cold packs. The diagnostic slides must be appropriately packed to prevent damage (e.g. slides should be placed in appropriate slide container) and placed in an individual plastic bag. It is also important that blocks are shipped in appropriately padded and secure containers to avoid physical damage. Do not wrap blocks or slides in tissue or paper toweling that is in direct contact with the paraffin.

The residual material will be forwarded for storage to the Alliance Biorepository at Washington University (WUSTL) by the laboratories performing the central pathology review and AR testing on a yearly basis. Please see Section 6.2.1 for contact information for WUSTL.

The Alliance has instituted special considerations for the small percentage of hospitals whose policy prohibits long-term storage of blocks, and the smaller percentage of hospitals whose policies prohibit release of any block. If, due to institutional policy, a block cannot be sent, 30 unstained slides at 5 micron thickness, or as many as possible if fewer than 30 (but at least 2 unstained slides) must be sent.

The goal of the Alliance Biorepository is to provide investigators with quality histology sections for their research while maintaining the integrity of the tissue. All paraffin blocks that are to be stored at the Alliance Biorepository will be vacuum packed to prevent oxidation and will be stored at 4° C to minimize degradation of cellular antigens. For these

reasons it is preferred that the Alliance Biorepository bank the block until the study investigator requests thin sections. Please contact the Alliance Biorepository if additional assurances with your hospital pathology department are required.

6.3.3 Whole Blood submission (for A091404-ST1)

For patients who consent to participate in blood collection, whole blood samples will be used for genomic studies described in Section 14.1. This sample should be collected prior to the initiation of protocol treatment.

Collect 1x10 mL of peripheral venous blood in an EDTA (lavender) tube. The tubes should be inverted several times to mix the EDTA and refrigerated until shipped on cool pack by overnight mail to the Alliance Biorepository at Washington University. The samples should be labeled with study number, patient ID number patient initials, sample collection date and time and be shipped the same day that the blood is drawn in room temperature with cold pack per Section 6.2.1.

6.3.4 Research tumor biopsies (for A091404-ST1)

For patients who consented to have the research biopsies of A091401-ST1, research tumor biopsies will be performed prior to initiation of enzalutamide and/or at the time of tumor progression (except for those that discontinue therapy for unacceptable toxicities). Radiologic guidance (CT, MRI or ultrasound guided) approaches and obtaining multiple cores to ensure sufficient biopsy material (at least 3 cores; optimally 4 to 6 cores preferred) is encouraged as long as it is considered reasonably safe for the patient. The tissues will be flash frozen immediately. If sufficient tissue is available, 1-2 core biopsies will also be fixed in formalin and submitted together with the flash frozen tissue. It is important that samples are frozen or fixed within 30 minutes of removal from the patient. All samples should be labeled with institutional surgical pathology number (tumor samples), study number, patient ID number patient initials, sample collection date and time, and should be shipped on dry ice with overnight service to the Alliance biorepository at Washington University according per Section 6.2.1.

7.0 TREATMENT PLAN/INTERVENTION

Enzalutamide will be given 160 mg orally once daily (1 cycle= 28 days). Dose interruptions and reductions are detailed in protocol Section 8.2. Patients will remain on therapy until progression of disease or development of unacceptable toxicities or patient or physician withdrawal.

Protocol treatment is to begin ≤ 7 days of registration.

It is acceptable for individual study drug doses to be delivered \leq a 24-hour (business day) window before and after the protocol-defined date for Day 1 of a new cycle. For example, if the treatment due date is a Friday, the window for treatment includes the preceding Thursday through the following Monday. In addition, patients are permitted to have a new cycle of chemotherapy delayed up to 7 days for major life events (e.g., serious illness in a family member, major holiday, vacation that cannot be rescheduled) without this being considered a protocol violation. Documentation to justify this delay should be provided.

To determine response via RECIST v1.1, patients will undergo radiographic imaging every 2 months (+/- 7 days) treatment for the first 8 cycles (beginning Day 1 Cycle 3) then every 3 cycles (beginning with Day 1 Cycle 9), until evidence of progression or relapse.

Agent	Dose	Route	Schedule
Enzalutamide	160 mg	PO	Daily

Note: If a patient is suspected to be pregnant, enzalutamide should be IMMEDIATELY discontinued and the study physician contacted. A positive urine test must be confirmed by a serum pregnancy test. If it is confirmed that the patients is not pregnant, the patient may resume dosing with enzalutamide.

7.1 CYP2C8 Inhibitors

Chronic concomitant treatment with strong inhibitors of CYP2C8 is not allowed on this trial. The following drug is an EXAMPLE of a strong inhibitor of CYP2C8 and is not allowed during treatment with enzalutamide:

Gemfibrozil

Because lists of these agents are constantly changing, please consult and review any drugs for their potential to inhibit CYP2C8. Examples of resources that may be utilized include the product information for the individual concomitant drug in question, medical reference texts, the FDA, or your local institution's pharmacist.

7.2 CYP3A4 Inducers

Chronic concomitant treatment with strong inducers of CYP3A4 is not allowed on this trial. The following drugs are EXAMPLES of a strong inducer of CYP3A4 and are not allowed during treatment with enzalutamide:

Rifampin

Carbamazepine

Because lists of these agents are constantly changing, please consult and review any drugs for their potential to induce CYP3A4 Examples of resources that may be utilized include the product information for the individual concomitant drug in question, medical reference texts, the FDA, or your local institution's pharmacist.

8.0 Dose and Treatment Modifications and management of toxicity

- 8.1 Ancillary therapy, concomitant medications, and supportive care
 - **8.1.1** Patients should not receive any other agent which would be considered treatment for the primary neoplasm or impact the primary endpoint. Exception: For patients who were previously treated with a luteinizing hormone-releasing hormone (LH-RH) agonist or antagonist, the LH-RH agonist or antagonist may be continued on this trial at the discretion of the attending physician.
 - **8.1.2** Patients should receive full supportive care while on this study. This includes blood product support, antibiotic treatment, and treatment of other newly diagnosed or concurrent medical conditions. All blood products and concomitant medications such as antidiarrheals, analgesics, and/or antiemetics received from the first day of study treatment administration until 30 days after the final dose will be recorded in the medical records
 - 8.1.3 Treatment with hormones or other chemotherapeutic agents may not be administered except for steroids given for adrenal failure; hormones administered for non-disease-related conditions (e.g., insulin for diabetes); intermittent use of dexamethasone as an antiemetic or for conditions that are not related to malignancy. Exception: For patients who were previously treated with a luteinizing hormone-releasing hormone (LH-RH) agonist or antagonist, the LH-RH agonist or antagonist may be continued on this trial at the discretion of the attending physician.
 - 8.1.4 Antiemetics may be used at the discretion of the attending physician, with the exception of steroids above.
 - 8.1.5 Diarrhea management is per the discretion of the treating physician. Diarrhea could be managed conservatively with medications such as loperamide.

Patients with severe diarrhea should be assessed for intravenous hydration and correction of electrolyte imbalances.

- 8.1.6 Palliative radiation therapy may not be administered during study enrollment.
 - Patients who require radiation therapy during protocol treatment will be removed from protocol therapy due to disease progression.
- **8.1.7 Surgery:** Patients who require surgery during protocol treatment may proceed as such, unless the surgery involves resection of salivary cancer. Study agent should be held prior to and after surgery, for a maximum of 28 days. If the patient requires an interruption of > 28 days, then they will be removed from protocol therapy.
- **8.1.8** Anticoagulation: Anticoagulation is allowed while on trial. Enzalutamide is a moderate CYP2C9 inducer, and drugs that are metabolized by CYP2C9 should be avoided, which includes warfarin. For patients who require warfarin therapy on trial, INR should be monitored closely while taking study agent. Utilization of other anticoagulation is recommended.
- **8.1.9 Hypertension:** Patients taking enzalutamide should maintain well-controlled blood pressure. The choice of medications used to control blood pressure is at the discretion of the treating physician.
- 8.1.10 Alliance Policy Concerning the Use of Growth Factors

The following guidelines are applicable unless otherwise specified in the protocol.

Blood products and growth factors should be utilized as clinically warranted and following institutional policies and recommendations. The use of growth factors should follow published guidelines of the American Society of Clinical Oncology 2015: Recommendations for the Use of WBC Growth Factors: American Society of Clinical Oncology Clinical Practice Guideline Update. J Clin Oncol , 2015.

Epoetin (EPO): Use of epoetin in this protocol is permitted at the discretion of the treating physician. The use of epoetin should follow published guidelines of the American Society of Clinical Oncology 2010 Update of Recommendations on the Use of Epoetin and Darbepoetin in Adult Patients with Cancer. J Clin Oncol 28(33): 4996-5010, 2010.

Filgrastim (G-CSF), tbo-filgrastim and sargramostim (GM-CSF)

- 1. Filgrastim (G-CSF)/tbo-filgrastim/pegfilgrastim and sargramostim (GM-CSF) treatment for patients on protocols that do not specify their use is discouraged.
- 2. Filgrastim/tbo-filgrastim/pegfilgrastim and sargramostim may not be used:
 - a. To avoid dose reductions, delays or to allow for dose escalations specified in the protocol.
 - b. For the treatment of febrile neutropenia the use of CSFs should not be routinely instituted as an adjunct to appropriate antibiotic therapy. However, the use of CSFs may be indicated in patients who have prognostic factors that are predictive of clinical deterioration such as pneumonia, hypotension, multi-organ dysfunction (sepsis syndrome) or fungal infection, as per the ASCO guidelines. Investigators should therefore use their own discretion in using the CSFs in this setting. The use of CSF (filgrastimtbo-filgrastim/pegfilgrastim or sargramostim) must be documented and reported.
 - c. If filgrastim/tbo-filgrastim/pegfilgrastim or sargramostim are used, they must be obtained from commercial sources.

8.1.11 Reproductive Considerations

See Sections 3.1 and 3.3.4 for details on teratogenicity of agents and reproductive considerations while on study agent. Please note that patients will need to continue pregnancy prevention for 3 months after discontinuation of study drug.

8.2 Dose Modifications

The following general guidelines apply to all dose modifications listed below

- Doses will not be re-escalated once reduced
- If dose reduction below dose level -2 is required, treatment with the agent will be discontinued.
- If treatment is held for more than four weeks due to toxicity, discontinue protocol therapy
- Each cycle is always 28 days regardless of dose interruption. (i.e., a 7 day interruption of a dose starting on day 15 of a cycle would mean that the dose is restarted on day 22 of the same cycle)
- If multiple adverse events are seen, administer dose based on greatest reduction required for any single adverse event observed. Reductions or increases apply to treatment given in the preceding cycle and are based on adverse events observed since the prior dose.

NOTE: AERS reporting may be required for some adverse events (See Section 9.0)

Dose level table for enzalutamide

Dose Level	enzalutamide
0 (starting dose)	160 mg/day
-1	120 mg/day
-2	80 mg/day

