8.2.1 Hepatic Toxicity

For ≥ grade 3 ALT or AST or Bilirubin (see Investigations in CTCAE v. 4.0), interrupt enzalutamide. Check liver function labs weekly. Restart enzalutamide at one dose level reduction when ALT, AST, and bilirubin recover to grade 1. Monitor serum transaminases and bilirubin every two weeks for three months and monthly thereafter.

For hepatic failure (see Hepatobiliary Disorders in CTCAE v. 4.0), discontinue enzalutamide.

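### Section 8.2 takes dose reductions from the preceding cycle's dose, so a second event within the restart cycle can literally repeat the current dose

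*Combined protocol and SAP*

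**What the plan says.** Section 7.0 gives enzalutamide at 160 mg once daily in 28-day cycles. The dose table in 8.2 adds level -1 (120 mg/day) and level -2 (80 mg/day).

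The bullets in 8.2 open with a statement of scope: "The following general guidelines apply to all dose modifications listed below". The last bullet has two sentences. The first is "If multiple adverse events are seen, administer dose based on greatest reduction required for any single adverse event observed". The second is "Reductions or increases apply to treatment given in the preceding cycle and are based on adverse events observed since the prior dose".

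Other bullets in the same list matter here:

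- Floor: "If dose reduction below dose level -2 is required, treatment with the agent will be discontinued".
- No return to a higher dose: "Doses will not be re-escalated once reduced".
- Longest hold: "If treatment is held for more than four weeks due to toxicity, discontinue protocol therapy".
- Cycles keep their 28 days when dosing is interrupted, and the example given is a restart without a change of cycle: "a 7 day interruption of a dose starting on day 15 of a cycle would mean that the dose is restarted on day 22".

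The toxicity-specific rules call for a step of one level. Section 8.2.1, for grade 3 or higher liver tests whatever the attribution, says "Check liver function labs weekly. Restart enzalutamide at one dose level reduction when ALT, AST, and bilirubin recover to grade 1". Section 8.2.4, for grade 3 or higher events attributed to enzalutamide, sets a hold of one week or until improvement to grade 2 or lower, and then allows a restart one level down. Neither section says which dose the level is counted from.

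**The concern.** A reference to the preceding cycle works when the dose is fixed for a whole cycle and changed only at the next one. Here the dose can change in mid-cycle, and the protocol's own example does this. The preceding cycle's dose may then be higher than the dose on which the new event occurred, and a step down from it can land on the dose the patient was already taking.

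A site applying the bullet as written would restart a patient on the dose that preceded the second event. For a patient already at 80 mg/day, it would continue treatment where the floor rule points to stopping. What is at stake is one consistent safety rule across sites, not the efficacy analysis.

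**Working it through.** **Inputs.** Dose levels 160, 120 and 80 mg/day, with discontinuation below 80 (8.2). Cycle length 28 days (7.0, 8.2). Holds of about one week are allowed (8.2.4), and liver tests are checked weekly during a hepatic hold (8.2.1).

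**The plan's own example.** A hold of h days from onset day d restarts on day d + h. With d = 15 and h = 7, 15 + 7 = 22, which is within 28. The restart on day 22 of the same cycle is reproduced.

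**Which dose is the reference?** Only the last bullet of 8.2 names one. Its second sentence is not limited to the multiple-event case, and the list applies to all modifications that follow.

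**When the literal rule repeats the dose.** Let the first restart at a reduced dose fall on day r of a cycle (cycle 2 or later), with the preceding cycle dosed at the higher level. A second event with onset d2 is held and restarted in that cycle if r ≤ d2 and d2 + h ≤ 28. The preceding cycle is then the same whether counted from onset or from restart.

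| Preceding cycle | First restart | Second restart, literal | Second restart, from current dose |
|---|---|---|---|
| 160 mg | 120 mg | 160 less one level = 120 mg | 120 less one level = 80 mg |
| 120 mg | 80 mg | 120 less one level = 80 mg | below level -2: discontinue |

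The no-re-escalation bullet does not prevent this, because repeating a dose is not an increase.

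**Examples, starting from 160 mg.**

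- *Both events in one cycle.* First event on day 3 of cycle 2; 3 + 7 = 10, restart at 120 mg. Second event on day 20; 20 + 7 = 27. Cycle 1 was at 160 mg, so the literal restart is 120 mg, against 80 mg.
- *First hold crosses a boundary.* First event on day 25 of cycle 2; 25 + 7 = 32, which is day 4 of cycle 3, restart at 120 mg. Second event on day 15; 15 + 7 = 22. Cycle 2 was at 160 mg, so the literal restart is again 120 mg, against 80 mg.

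**Where the reference is unclear.**

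- *Second hold crosses a boundary.* Same first event as in the last example, but the second is on day 23 of cycle 3; 23 + 7 = 30, which is day 2 of cycle 4. Counted from onset, the preceding cycle is cycle 2 (160 mg), giving 120 mg. Counted from restart, it is cycle 3 (120 mg), giving 80 mg.
- *Cycle 1.* An event held and restarted within cycle 1 has no preceding cycle.

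**Limit of the problem.** The longest permitted hold is 28 days. With h = 28 the condition d2 + 28 ≤ 28 has no solution for d2 ≥ 1, so the repeat needs a shorter second hold.

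**The case against.** **The specific rules already settle it.** A patient on 120 mg who restarts on 120 mg has had no reduction, so a site following 8.2.1 or 8.2.4 in their natural sense would go to 80 mg. This largely stands as a prediction of practice, and it is why the severity is low. It does not remove the conflict: those sections name no reference dose, and the general bullet names one and applies to them.

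**The sentence also refers to events since the prior dose, which points to recent dosing.** That clause says which events count. It does not say which dose the step is taken from.

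**The visit calendar explains the wording.** From cycle 2 on, scheduled assessments fall on Day 1 (Section 5.0), when the preceding cycle's treatment is what the patient has just taken. For a stable dose this is fair. A hepatic event found on Day 1 and restarted on day 8 reaches its two-weekly check on day 22 (8 + 14); the next weekly check is day 29, already the next cycle. Scheduled testing can still produce the problem. Take a hepatic event found at the day 15 visit of cycle 1 that recovers at the second weekly check: 15 + 14 = 29, which is day 1 of cycle 2, restart at 120 mg. The two-weekly check is day 15 of cycle 2 (1 + 14). If that is again grade 3 and recovers in a week, the restart is on day 22 (15 + 7), and the literal dose is 120 mg because cycle 1 was at 160 mg.

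**Repeating the dose might be deliberate, given the 5.8-day half-life in 10.1.** Nothing in 8.2 offers this as a reason.

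**A reader might infer that 8.2 as a whole plainly orders the repeat dose, or that many patients would receive it.** The documents support neither. The specific sections, naturally read, point the other way, and no rate is given for two such events. Counting the onset days that fit the condition would measure positions on a calendar, not risk.

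**Conclusion.** The last bullet of 8.2 is wrong as written, at low severity. In a cycle from cycle 2 on where a patient has restarted at a reduced dose, a second event needing a reduction that is held and restarted in that cycle literally leaves the dose unchanged: 120 mg/day instead of 80 mg/day, or 80 mg/day instead of discontinuation. That contradicts the floor rule, and the one-level step of 8.2.1 and 8.2.4 if the step is counted from the current dose. For events held and restarted within cycle 1, and for second holds that cross into a new cycle, the text is unclear and no stronger statement is warranted.

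The conclusion rests on two readings: that the reference-dose sentence applies to all modifications, as the opening of 8.2 says, and that a one-level reduction is meant from the dose in use. The scenario is uncommon and its frequency cannot be estimated from the documents.

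The mention of increases contradicts the no-re-escalation bullet. A reader might infer that it permits a dose increase, but that bullet forbids one, so no dose changes. Nor do the documents support an inference that the trial's result is affected: the two-stage design, sample size and analyses do not depend on this rule.

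**What to change.** Keep the sentence on the greatest required reduction. Replace the sentence after it with:

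*Reductions are made from the dose the patient was taking when the adverse event occurred (or, if it began during a hold, the last dose taken before the hold), and reflect adverse events observed since that dose level was started; if that dose was 80 mg/day, discontinue enzalutamide.*

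This supplies a reference dose in cycle 1 and across cycle boundaries, keeps a statement of which events count, and removes the mention of increases. The 80 mg clause restates the existing floor at the point of use. The sentence governs reductions only, so a hold that ends without one, such as RPLS ruled out under 8.2.3, is unaffected.

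The cost is one sentence in 8.2, with no added patients, visits or data.
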